3.2.7 Proportion alive and progression free at 12 (APF12) and 18 (APF18) months

APF12 will be defined as the Kaplan-Meier (KM) estimate of PFS (per RECIST 1.1, using Investigator assessment) at 12 months. Similarly, APF18 will be defined as KM estimate of PFS at 18 months.

3.2.8 Overall survival at 12 (OS12) and 24 (OS24) months

OS12 will be defined as the KM estimate of OS at 12 months. Similarly, OS24 will be defined as the KM estimate of OS at 24 months.

3.3 Safety Variables

Safety and tolerability will be assessed in terms of AEs (including serious adverse events [SAEs]), deaths, laboratory data, vital signs, ECGs, physical examinations and exposure. These will be collected for all patients.

The Safety analysis set (SAS) will be used for reporting of safety data.

On-treatment is defined as assessment where the date and time of the assessment is the same as or greater than the date and time of first treatment with either tremelimumab or durvalumab and up to (and including) 90 days after the last dose date of tremelimumab or durvalumab. For vital signs, On-treatment is defined as assessment where the date of first treatment with either tremelimumab or durvalumab and update (including) 30 days after the last dose date of tremelimumab or durvalumab.

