9.4.2 Calculation or derivation of safety variables

9.4.2.1 Adverse events

Safety and tolerability will be assessed in terms of AEs (including SAEs), deaths, laboratory data, vital signs, ECGs, physical examinations and exposure. These will be collected for all patients. Data from all cycles of treatment will be combined in the presentation of safety data. For AEs, on treatment (or treatment-emergent AEs) will be defined as any AEs that started after dosing or prior to dosing and which worsens following exposure to the treatment.

Adverse events observed up until 90 days following discontinuation of the immunotherapy agents (ie, the last dose of durvalumab, tremelimumab or durvalumab + tremelimumab) or until the initiation of the first subsequent therapy following discontinuation of treatment (whichever occurs first) will be used for the reporting of the AE summary tables. This will more accurately depict AEs attributable to study treatment only as a number of AEs up to 90 days following discontinuation of the immunotherapy agents are likely to be attributable to subsequent therapy. However, to assess the longer term toxicity profile, AE summaries will also be produced containing AEs observed up until 90 days following discontinuation of the immunotherapy agents (ie, without taking subsequent therapy into account). Any events in this period that occur after a patient has received further therapy for cancer (following discontinuation of study treatment) will be flagged in the data listings.

The SAS will be used for reporting of safety data.

A separate data listing of AEs occurring more than 90 days after discontinuation of IP will be produced. These events will not be included in AE summaries.

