3.3.1 Adverse Events

AEs will be assigned to the following periods related to date and time of onset of the AEs relative to first and last dose dates of study treatment and the date of starting any subsequent anti-cancer therapy post-discontinuation of study treatment.

AE occurrence	Period Assigned
Date before first treatment with either durvalumab or tremelimumab	Pre-treatment
Date the same as or greater than the date of first treatment with durvalumab or tremelimumab, either as monotherapy or combination therapy (or date before first treatment, but worsening following first dose) and up to (and including) 90 days after the last dose date of durvalumab or tremelimumab, or initiation of the first subsequent anti-cancer therapy following discontinuation of study treatment (whichever occurs first)	On-treatment, prior to subsequent anti-cancer therapy
Date the same as or greater than the date of first treatment with durvalumab or tremelimumab, either as monotherapy or combination therapy (or date before first treatment, but worsening following first dose) and up to (and including) 90 days after the last dose date of durvalumab or tremelimumab	On-treatment
Date after initiation of the first subsequent anti-cancer therapy following discontinuation of study treatment up to (and including) 90 days after the last dose date of durvalumab or tremelimumab	On-treatment Post-subsequent anti-cancer therapy
Date more than 90 days after the last dose date of either durvalumab or tremelimumab	Post-study treatment

AE Adverse event.

AEs that have missing causality (after data querying) will be assumed to be related to study treatment.

The latest version of the Medical Dictionary for Regulatory Activities (MedDRA) will be used to code the AEs. AEs will be graded by the Investigator according to the latest version of the National Cancer Institute Common Terminology Criteria for AEs (CTCAE).

AEs of special or possible interest

Some clinical concepts (including some selected individual preferred terms [PTs] and higher-level terms [HTLs]) have been considered “AEs of special interest” (AESI) or “AEs of possible interest” (AEPI) to the durvalumab program. AESI/AEPIs represent pre-specified risks that are considered to be of importance to a clinical development program.

These AESI/AEPIs have been identified as a list of categories provided by the patient safety team.

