3.3.2 Laboratory data

Blood and urine samples for determination of clinical chemistry, hematology, and urinalysis will be taken at the times indicated in the assessment schedules and as clinically indicated Sections 1.1 and 8.2.1 of the CSP.

Change from baseline in hematology and clinical chemistry variables will be calculated for each post-dose visit on treatment. CTCAE grades will be defined at each visit according to the CTCAE grade criteria using local ranges as required, after conversion of lab result to corresponding preferred unit. The following parameters have NCI CTCAE grades defined for both high and low values: Hemoglobin, Leukocytes, Lymphocytes, Potassium, Sodium, Magnesium and Corrected calcium so high and low CTC grades will be calculated.

Absolute values will be compared to the local laboratory reference ranges and classified as low (below range), normal (within range or on limits of range) and high (above range).

The maximum or minimum on-treatment value (depending on the direction of an adverse effect) will be defined for each laboratory parameter as the maximum (or minimum) post-baseline value at any time.

Corrected calcium product will be derived during creation of the reporting database using the following formula:

$$\text{Corrected calcium (mmol/L)} = \text{Total calcium (mmol/L)} + ([40 - \text{albumin (G/L)}] \times 0.02)$$

Project reference ranges will be used for the primary interpretation of laboratory data. Local reference ranges will be used for analysing laboratory data at the local laboratory. The denominator used in laboratory summaries of CTCAE grades will only include evaluable patients, in other words those who had sufficient data to have the possibility of an abnormality.

For example:

- If a NCI CTCAE criterion involves a change from baseline, evaluable patients would have both a pre-dose and at least 1 post dose value recorded.
- If a NCI CTCAE criterion does not consider changes from baseline to be evaluable, the patient need only have 1 post dose value recorded.

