4.1.3 Time Windows

Safety assessments

Time windows will need defining for any presentations that summarize values by visit. The following conventions apply:

- The time windows should be exhaustive so that data recorded at any time point has the potential to be summarized. Inclusion within the time window should be based on the actual date and not the intended date of the visit.
- All unscheduled visit data should have the potential to be included in the summaries.
- The window for the visits following baseline will be constructed in such a way that the upper limit of the interval falls halfway between the two visits (the lower limit of the first post-baseline visit will be Day 2). If an even number of days exists between two consecutive visits, then the upper limit will be taken as the midpoint value minus 1 day. For example, the visit windows for vital signs data in the dose-expansion phase for patients' treatment with durvalumab in combination with tremelimumab are:
 - Cycle 1 Day 8 visit window day 2-11
 - Cycle 1 Day 15 visit window day 12 - 21
 - Cycle 2 Day 1 visit window day 22 - 35
 - Cycle 2 Day 15 visit window day 36 - 49
 - Cycle 3 Day 1 visit window day 50 – 63
 - etc
- The upper limit for the last record on treatment will consider end of treatment date and not date of disease progression.
- For summaries showing the maximum or minimum values, the maximum/minimum value recorded on treatment will be used (regardless of where it falls in an interval).
- Listings should display all values contributing to a time point for a patient.
- For visit based summaries:
 - If there is more than one value per patient within a time window then the closest value to the scheduled visit date should be used, or the earlier in the event the values are equidistant from the nominal visit date. The listings should highlight the value for that patient that went into the summary table, wherever feasible. Note: in summaries of extreme values all on-treatment values collected are used including those collected at unscheduled visits.
 - To prevent very large tables or plots being produced that contain many cells with meaningless data for outputs in the dose expansion phase, for each treatment group visit data should only be summarized if the number of observations is greater than the minimum of 5 of patients dosed.

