4.2.3.3 Clinical laboratory variables (clinical chemistry, hematology and urinalysis)

All laboratory safety data will be listed for each patient and summarized where appropriate. Clinical chemistry and hematology values outside the reference ranges will be highlighted in the listings. Data summaries will be provided in preferred units.

For continuous laboratory data absolute and change from baseline will be summarized by visit.

Box plots of change from baseline will be presented for haematology and clinical chemistry variables.

Shift tables for laboratory values by worst CTCAE grade will be produced, and for specific parameters separate shift tables indicating hyper- and hypo- directionality of change will be produced. The laboratory parameters for which CTCAE grade shift outputs will be produced are:

- Hematology: Hemoglobin (low and high), Leukocytes (low and high), Lymphocytes (low and high – absolute count), Neutrophils (low – absolute count), Platelets.
- Clinical chemistry: ALT (high), AST (high), ALP (high), Total bilirubin (high), Albumin (low), Magnesium (hypo and hyper), Sodium (hypo and hyper), Potassium (hypo and hyper), Corrected calcium (hypo and hyper), Glucose (low), Creatinine (high).

For urinalysis a shift table comparing baseline to the maximum on-treatment value will be presented.

Hy's law

The following summaries will include the number (%) of patients who have:

- Elevated ALT, AST, and Total bilirubin during the study
 - ALT $\geq 3\times$ - $\leq 5\times$, $> 5\times$ - $\leq 8\times$, $> 8\times$ - $\leq 10\times$, $> 10\times$ - $\leq 20\times$, and $> 20\times$ Upper Limit of Normal (ULN) during the study
 - AST $\geq 3\times$ - $\leq 5\times$, $> 5\times$ - $\leq 8\times$, $> 8\times$ - $\leq 10\times$, $> 10\times$ - $\leq 20\times$, and $> 20\times$ ULN during the study
 - Total bilirubin $\geq 2\times$ - $\leq 3\times$, $> 3\times$ - $\leq 5\times$, $> 5\times$ ULN during the study
 - ALT or AST $\geq 3\times$ - $\leq 5\times$, $> 5\times$ - $\leq 8\times$, $> 8\times$ - $\leq 10\times$, $> 10\times$ - $\leq 20\times$ and $> 20\times$ ULN during the study
 - ALT or AST $\geq 3\times$ ULN and Total bilirubin $\geq 2\times$ ULN during the study (potential Hy's law). Note: Note: The onset date of ALT or AST elevation should be prior to or on the date of total bilirubin elevation.

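### Laboratory worst-value tables have no version that stops at subsequent anticancer therapy, although the AE tables do, so values drawn on the next treatment can set a patient's worst grade

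*SAP*

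**What the plan says.** **Laboratory data.** SAP 3.3 gives one general on-treatment definition: from first dose "up to (and including) 90 days after the last dose date of tremelimumab or durvalumab". Vital signs have their own shorter limit, "30 days after the last dose date of tremelimumab or durvalumab". Laboratory data have none and fall under the general rule. SAP 3.3.2 is looser: the on-treatment extreme "will be defined for each laboratory parameter as the maximum (or minimum) post-baseline value at any time". SAP 4.1.3 lets any on-treatment value supply the maximum or minimum, whichever visit window it falls in. SAP 4.2.3.3 states "Shift tables for laboratory values by worst CTCAE grade will be produced" without naming a window, and counts ALT, AST, bilirubin and potential Hy's law thresholds over the whole study.

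**AEs.** SAP 3.3.1 defines one on-treatment period that ends at the first subsequent anticancer therapy if that comes before 90 days, and a second that runs the full 90 days. SAP 4.2.3.2 summarizes AEs separately by period. Protocol 9.4.2.1 asks for both versions and gives the reason for the cut: "a number of AEs up to 90 days following discontinuation of the immunotherapy agents are likely to be attributable to subsequent therapy". It also asks for AEs after further cancer therapy to be flagged in listings.

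**Sampling.** Protocol Table 3 schedules hematology, clinical chemistry and TSH at day 30, month 2 and month 3 after last dose. It makes no exception for patients who have started another therapy.

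**The concern.** The protocol's argument for cutting AEs at the next therapy applies equally to cytopenias and transaminase rises, which many later regimens could cause. Neither Protocol 9.4.2.2 nor the SAP carries the argument over to laboratory data, and SAP 6 gives no reason for the difference.

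The AE tables do not fill the gap. Under Protocol 8.3.7, a deterioration in a protocol-mandated laboratory value is reported as an AE in its own right only if it meets a seriousness criterion or is the reason for stopping study drug. Asymptomatic laboratory toxicity is therefore seen mainly in the laboratory tables.

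Laboratory evaluations are endpoints of the primary safety objective in dose-finding and of the safety objective in dose-expansion. If a worst grade reached on another regimen is tabulated as on-treatment, the hematological and hepatic profile of durvalumab plus tremelimumab looks worse than it was.

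**Working it through.** There is no figure in the plan to reproduce. The check sets the rules side by side, then counts which scheduled samples each one admits.

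**1. End of the window for each output**

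| Output | Source | End of window | Version cut at next therapy? |
|---|---|---|---|
| AEs, version 1 | SAP 3.3.1 | earlier of 90 days and next therapy | yes |
| AEs, version 2 | SAP 3.3.1 | 90 days | no |
| Vital signs | SAP 3.3 | 30 days | no |
| Laboratory, general | SAP 3.3 | 90 days | no |
| Laboratory maximum/minimum | SAP 3.3.2 | none stated | no |
| Worst-grade shift tables | SAP 4.2.3.3 | none stated | no |
| Liver thresholds | SAP 4.2.3.3 | whole study | no |
| Laboratory by-visit summaries | SAP 4.1.3, 6 | end of treatment | not needed |

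Every laboratory extreme-value row admits samples taken after a switch.

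**2. Scheduled samples inside the 90-day window.** Table 3 nominal days after last dose, with a month taken as 30 days (its footnote equates 3 months with 90 days), are 30 (±3), 60 (±7) and 90 (±7).
- The latest day-30 sample is 30 + 3 = 33, inside.
- The latest month-2 sample is 60 + 7 = 67, inside.
- The latest month-3 sample is 90 + 7 = 97, outside if drawn after day 90.

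So three sets enter, or two if the month-3 visit is late. The 30-day limit used for vital signs would admit at most one.

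**3. Sets drawn on the next therapy, by start date (nominal days)**

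| Next therapy starts, days after last dose | Post-switch sets in window |
|---|---|
| before 30 | 3 |
| 30 to before 60 | 2 |
| 60 to before 90 | 1 |
| 90 or later | 0 |

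With the cut used for AE version 1, each entry becomes 0.

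**4. Weight of one patient.** Using the planned evaluable numbers in SAP 1.3, 1/26 = 3.8 percentage points in SARCOMA and 1/10 = 10 points in STO. The tables use the safety analysis set, which can be somewhat larger, so these are approximate.

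**5. Illustrative range; every input is assumed.** Let s be the share who start another therapy within 90 days and have a later sample, c the share of those who reach a new worst grade on it, and b the share who already had that grade. The affected share is s × c × (1 − b). With b = 0.15:
- Low (s = 0.20, c = 0.30): 0.20 × 0.30 × 0.85 = 5.1%, or 1.3 of 26 and 0.5 of 10.
- High (s = 0.60, c = 0.70): 0.60 × 0.70 × 0.85 = 35.7%, or 9.3 of 26 and 3.6 of 10.

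The width shows that the size cannot be settled from the documents.

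**The case against.** **The AE comparison is closer than it looks.** A reader might infer that the laboratory tables cannot match the AE tables. That is not so: the uncut AE period in SAP 3.3.1 has the same 90-day limit as SAP 3.3. What is missing is the laboratory counterpart of the cut version.

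**There is no departure from the protocol.** Protocol 9.4.2.1 states its cut for AE summaries, and 9.4.2.2 sets none for laboratory data. This stands. The point extends the sponsor's own reasoning and does not correct a breach.

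**The tables assign no causality.** SAP 4.2.3 makes safety summaries descriptive, the trial has no comparator, and all laboratory data are listed. This stands, so the tables can overstate toxicity but do not formally attribute it. No flag for post-switch laboratory values is specified, however.

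**End of treatment may be the real limit.** SAP 4.1.3 and 6 use it, but SAP 6 confines it to visit windowing, and 4.1.3 frees maximum and minimum summaries from visit intervals. Different scopes for by-visit and extreme-value displays are a design choice, not in themselves a contradiction. If the limit was meant for all laboratory outputs, SAP 3.3 and 3.3.2 say otherwise and need changing.

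**Few post-switch samples may exist.** The synopsis says that patients who have begun another therapy are followed for PK and survival. This may reduce the number, but Table 3 does not cancel the visits, and Protocol 7.1.1 keeps discontinued patients on scheduled visits.

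**A cut could hide delayed immune toxicity.** Protocol 8.3.2 expects that late-onset toxicity may occur. This is the strongest objection, and it is why the uncut version must stay.

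**Conclusion.** The concern holds as a gap in the planned laboratory outputs. As written, samples taken after a new anticancer therapy can set the worst laboratory grade, and no planned table shows the profile without them. Up to three scheduled sets per patient are exposed, fewer with a later switch or a late month-3 visit.

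The effect on reported grades is unknown. The documents give no switching rate and no toxicity rate for later regimens. A reader might take the median PFS of 1.8 months in the pediatric pembrolizumab study cited in Protocol 2.2.1 as evidence of early switching. PFS is not time on treatment, though, and Protocol 8.1 continues dosing from first progression to its confirmation, absent clinically significant deterioration. Nor do the documents support a claim that the tables will misstate toxicity by any given amount.

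The conclusion assumes that Table 3 sampling continues after a switch. The primary response analysis is unaffected. The change is worth making because, in cohorts this small, one or two patients visibly move a safety proportion.

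**What to change.** - In SAP 3.3, add a laboratory on-treatment period ending at the earlier of 90 days after last dose and the start of the first subsequent anticancer therapy.
- In SAP 3.3.2 and 4.2.3.3, produce the worst-grade shift, maximum/minimum and liver-threshold tables for that period.
- Keep an uncut 90-day version of the same tables alongside, as Protocol 9.4.2.1 does for AEs, so that delayed immune-mediated toxicity remains visible.
- Replace the open-ended wording in 3.3.2 and the whole-study wording in 4.2.3.3 with these two windows. Editing 3.3 alone would leave both in force.
- Flag values drawn after the switch in the laboratory listings.

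The cost is SAP text in three sections, one date condition in programming and a second set of laboratory tables. No new data are needed: Table 3 already requires the start date of subsequent therapy.

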3.3.1 Adverse Events

AEs will be assigned to the following periods related to date and time of onset of the AEs relative to first and last dose dates of study treatment and the date of starting any subsequent anti-cancer therapy post-discontinuation of study treatment.

AE occurrence	Period Assigned
Date before first treatment with either durvalumab or tremelimumab	Pre-treatment
Date the same as or greater than the date of first treatment with durvalumab or tremelimumab, either as monotherapy or combination therapy (or date before first treatment, but worsening following first dose) and up to (and including) 90 days after the last dose date of durvalumab or tremelimumab, or initiation of the first subsequent anti-cancer therapy following discontinuation of study treatment (whichever occurs first)	On-treatment, prior to subsequent anti-cancer therapy
Date the same as or greater than the date of first treatment with durvalumab or tremelimumab, either as monotherapy or combination therapy (or date before first treatment, but worsening following first dose) and up to (and including) 90 days after the last dose date of durvalumab or tremelimumab	On-treatment
Date after initiation of the first subsequent anti-cancer therapy following discontinuation of study treatment up to (and including) 90 days after the last dose date of durvalumab or tremelimumab	On-treatment Post-subsequent anti-cancer therapy
Date more than 90 days after the last dose date of either durvalumab or tremelimumab	Post-study treatment

AE Adverse event.

AEs that have missing causality (after data querying) will be assumed to be related to study treatment.

The latest version of the Medical Dictionary for Regulatory Activities (MedDRA) will be used to code the AEs. AEs will be graded by the Investigator according to the latest version of the National Cancer Institute Common Terminology Criteria for AEs (CTCAE).

AEs of special or possible interest

Some clinical concepts (including some selected individual preferred terms [PTs] and higher-level terms [HTLs]) have been considered “AEs of special interest” (AESI) or “AEs of possible interest” (AEPI) to the durvalumab program. AESI/AEPIs represent pre-specified risks that are considered to be of importance to a clinical development program.

These AESI/AEPIs have been identified as a list of categories provided by the patient safety team.

AESI/AEPIs include but are not limited to events with a potential inflammatory or immune-mediated mechanism and which may require more frequent monitoring and/or interventions such as steroids, immunosuppressants and/or hormone replacement therapy. These AESI/AEPIs are being closely monitored in clinical studies with durvalumab monotherapy and combination therapy.

AESI/AEPIs observed with durvalumab ± tremelimumab include but are not limited to:

- Diarrhea/colitis and intestinal perforation
- Pneumonitis/ interstitial lung disease
- Endocrinopathies (i.e. events of hypophysitis/hypopituitarism, adrenal insufficiency, hyper and hypothyroidism and type I diabetes mellitus)
- Hepatitis/transaminase increases
- Nephritis/blood creatinine increases
- Pancreatitis/serum lipase and amylase increases
- Rash/dermatitis
- Myocarditis
- Myositis/polymyositis
- Other inflammatory responses that are rare/less frequent with a potential immune-mediated etiology include, but are not limited to, pericarditis, sarcoidosis, uveitis, and other events involving the eye, skin, hematological, and rheumatological events.

In addition, infusion-related reactions and hypersensitivity/anaphylactic reactions with a different underlying pharmacological etiology are also considered AESIs.

Other categories may be added as necessary or existing terms may be merged. An AstraZeneca medically qualified expert after consultation with the Global Patient Safety Physician has reviewed the AEs of interest and identified which HLTs and which PTs contribute to each AESI/AEPI. Further reviews may take place prior to database lock to ensure any further terms not already included are captured within the categories.

Immune-Mediated Adverse Events (imAE)

Sponsor will perform medical review of those AESIs and classify them as immune-mediated AEs (imAEs) or not imAEs. Further details are provided in an imAE Charter.

